PARTNERS HUMAN RESEARCH COMMITTEE PROTOCOL SUMMARY

Answer all questions accurately and completely in order to provide the PHRC with the relevant information to assess the risk-benefit ratio for the study. Do not leave sections blank.

PRINCIPAL/OVERALL INVESTIGATOR

[name]

PROTOCOL TITLE

Promoting informed decisions about rescheduling colonoscopies delayed due to COVID-19 (PRIMED-2): randomized controlled trial

FUNDING

Patient Centered Outcomes Research Institute (PCORI)

VERSION DATE

January 6, 2021

SPECIFIC AIMS

Concisely state the objectives of the study and the hypothesis being tested.

Due to COVID-19 there has been a sharp reduction in the number of colonoscopies since Feb 2020. This is predicted to lead to delayed diagnosis in more than 18,000 patients across the US.ⁱ Recovery efforts are underway to plan for resuming these non essential health care services. However, if patients are not willing or able to come back to get routine cancer screening, then these testing delays may have a significant impact on cancer mortality rates. There is very limited data examining patients' attitudes and concerns about seeking cancer screening in this environment. The aims of this study are to:

Aim 1: Assess anxiety, COVID risk tolerance, cancer worry, willingness to screen, barriers to colonoscopy, and preference for alternative colon cancer screening options for patients aged 45-75 who had their screening or surveillance colonoscopy delayed due to the pandemic.

Aim 2: Examine effectiveness of using a shared decision making approach with patients on the waitlist to decide about rescheduling their colonoscopy. We will randomly assign patients to receive SDM tools or usual care. We will test hypotheses that compared to the control group, patients in intervention arm will (a) report higher shared decision making; (b) have stronger intention to follow through with colon cancer screening (whether colonoscopy, stool-based test or other approach); and (c) have less decisional conflict.

Aim 3: Follow all patients on the waitlist and examine wait times and completed colonoscopies to determine whether these differ by patient characteristics, including gender, age, race and ethnicity, adjusting for cancer risk.

BACKGROUND AND SIGNIFICANCE

Provide a brief paragraph summarizing prior experience important for understanding the proposed study and procedures.

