For Aim 2, we will conduct a randomized controlled trial that will enroll patients who have to reschedule colonoscopies. We will randomly assign about 900 patients who are on the waitlist to either intervention or control arm. The intervention arm will receive a shared decision making worksheet that will cover (a) presenting pros and cons of three screening options (first available colonoscopy (wait time estimated to be ~6 months), stool-based test (with consideration that if positive, a follow-up colonoscopy may still be delayed ~3 months), and delay colonoscopy one year); (b) contact information for rescheduling their colonoscopy; and (c) contact information to connect with staff if they have questions or need more information. GI clinicians will be recruited and complete an online SDM training prior to their visit with patients who have more questions and request a GI visit. The control group will receive the standard department guidance and policies on scheduling. We will invite patients to complete a survey to track SDM, decisional conflict, overall anxiety and cancer worry, preference for colonoscopy, concerns about accessing health care-and we will also track any testing received within 6 months. We estimate sending a survey to about 700 patients across both arms and receiving 450 completed surveys.

For Aim 3, we will follow all MGH patients who had their screening or surveillance colonoscopy delayed for 12 months and will document receipt of colonoscopy or other colon cancer screening test, and if they got a colonoscopy, will calculate the wait time for colonoscopy for all of the patients on the waitlist. We will track demographic information, age, gender, race and ethnicity, primary language, zip code. We estimate that there are about 5,000 patients who have had their colonoscopy delayed that will be followed in this chart review portion of the study.

Table 1: Eligibility for patient participants

Eligible	Ineligible

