There are minimal risks to participating individuals associated with or attributable to this study. The main risks are associated with loss of privacy of their health information. To minimize risks, all electronic data files that include patient identifiers will be kept in a Partners protected server and only members of the research team will have access to the files. Files with PHI will only be accessed from Partners computers or encrypted laptops that are protected with SafeBoot. To ensure confidentiality, all paper surveys will be identified by study code number only and kept in a locked file cabinet. All paper surveys will be scanned and electronic files will be stored on password protected Partners server. Study papers (e.g. eligibility screeners, surveys) that have been scanned or entered into a database will be disposed of in the confidential shredder. To address issues of psychological discomfort, research assistants will inform patients that they may refuse to answer any question and may withdraw from the study at any time. To address privacy and confidentiality issues, analytic database with outcomes data will not contain any identifying information and will be coded by unique study ID number only.

Describe explicitly the methods for ensuring the safety of subjects. Provide objective criteria for removing a subject from the study, for example, objective criteria for worsening disease/lack of improvement and/or unacceptable adverse events. The inclusion of objective drop criteria is especially important in studies designed with placebo control groups.

Although there are no written informed consent forms, Drs. [name] and [name] are responsible for assuring that patient participants are adequately informed prior to engaging in any research procedures, that all subjects meet eligibility criteria, and that the study is conducted according to the IRB-approved research plan.

There are no formal stopping rules for this minimal risk study.

FORESEEABLE RISKS AND DISCOMFORTS

Provide a brief description of any foreseeable risks and discomforts to subjects. Include those related to drugs/devices/procedures being studied and/or administered/Performed solely for research purposes. In addition, include psychosocial risks, and risks related to privacy and confidentiality. When applicable, describe risks to a developing fetus or nursing infant.

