- [name] will follow up on the Chief's communication and will reach out individually to clinicians via email and/or during regular meetings to describe the study and invite clinicians to join. The email will contain an information sheet for clinicians.
- Clinicians will indicate consent by sending an email to [name] and/or [name] indicating their interest to join the study.
- Interested clinicians will complete a ~1 hour online shared decision making training session with study investigators and send availability for ~1 hour per week they may be available to meet with study participants who request a GI visit via the intervention.
- All clinician participants will complete a short phone debrief after the intervention is complete and receive a thank you email.

Patient recruitment, Aim 2:

- Study staff will work with the GI department to identify patients whose colonoscopy has been delayed due to COVID-19 and meet the eligibility criteria in Table 1.
- Study statistician will randomly assign patients on the waiting list to either the intervention or control group. Patients in the intervention group will receive information in the mail that describes available options for colon cancer screening and directions on who to call depending on patients' preference for screening. The usual care group will not receive the information.
- About 6-8 weeks after the mailing, the research coordinator will send a survey packet that includes: a cover letter signed by the Director of Quality and Safety for the department inviting their participation, an information sheet describing the study, an incentive (\$10), and the survey. The cover letter will have information for participants who wish to opt out of the survey. Patients will be given the option to complete the survey by RedCap and a link will be included in the cover letter. Patient consent for the study will be implied by return of the completed survey.

- Staff will make up to three reminder phone calls. Study staff will send all non responders, who did not opt-out, one reminder paper survey packet about four weeks after the initial packet. Study staff will then make up to 3 additional reminder calls to non-responders.
- All participants who complete a survey will receive a thank you note.

All study staff are CITI certified and will receive training from the PI and program manager in the study protocol. We will hold regular meetings to review screening, enrollment and completion data.

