The intervention mailings went out in four waves, about two weeks apart, between September 10, 2020 and October 22, 2020. Participants in the intervention arm received a decision worksheet in the mail followed by a call from a decision coach. A subset of participants across both arms were selected to receive a survey. Staff mailed a survey to the selected subset of control and intervention participants about 8 weeks after the intervention packet was mailed to their wave. The survey packet included a cover letter, an information sheet, an incentive (\$10 gift card), the survey and a return envelope. Patients were able to complete the survey by mail, online via REDCap, or over the phone with study staff. Staff made up to three reminder phone calls and sent a reminder mailing to non-responders with 3 additional reminder calls. Spanish-speaking research staff conducted reminder calls for Spanish-speaking participants. Staff conducted chart review to collect screening tests completed within 6 months.

Randomization and blinding: The study statistician used a computer random number generator to randomly select 800 eligible patients, assign each to intervention or control arm, and to one of 4 waves. All 800 patients were followed to track colon cancer screening tests completed and a subset in each wave were randomly selected to receive a survey to measure patient-reported outcomes. The staff who entered the data from the paper surveys and who conducted chart review to collect screening were blinded to the assignment. The statistician analyzing the results was not blinded to the assignment.

Outcomes:

Screening uptake: study staff examined medical records to determine receipt of any colorectal cancer screening test for all subjects within 6 months.

The following measures were collected in the patient survey:

SDM Process Scale: 4-item survey asks about discussion of stool test, pros and cons of colonoscopy and patient's screening preference. Total scores range from 0-4 with higher scores indicating higher shared decision making. Patients who indicated that they did not talk with anyone about CRC screening received a SDM Process score of 0.

SURE scale: the brief 4-item version of the decisional conflict scale. A point is given for each "yes" response for total scores 0-4 and we report the percentage receiving the top score of 4, which indicates no decisional conflict.

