Screening preference: One item asked patient's preferred approach to screening (with responses: colonoscopy, stool-based test, delay screening, not sure).

Additional measures were collected to describe the sample and used as covariates including whether or not the patient had a CRC discussion with health care provider in the past two months, PROMIS Scale v1.2-Global Health Physical 2a, Single Item Literacy Screener, CRC screening and history, COVID-19 worry, decision worksheet use and decision coaching exposure. Basic demographics for the full sample were collected via chart review.

Sample Size: The sample size of 800 was determined based on the screening uptake, with 800 participants, the study had 81% power to detect a difference of 10% in rates. For the survey, we assumed a 60% response rate and as a result, planned to invite about 500 patients (250 in each arm) to obtain 300 responses. With 300 survey responses, the study had 80% power to detect a difference of 0.32 standard deviation (SD) for the SDM Process score. Studies have found effect sizes ranging from 0.39SD – 0.88SD for SDM Process when comparing sites that used formal

decision support (coaching or decision aids) and those that did not. For dichotomized survey outcomes (% SURE top score and % prefer screening), with 300 responses, we had 80% power to detect a 13% difference, from 70% to 83%.

Statistical methods: Sample demographics and characteristics were compiled and compared to evaluate the balance between the two arms. Responders and non-responders to the survey were compared between arms to evaluate potential non-response bias.

The following hypotheses were evaluated using an intention to treat approach, and patients were analyzed based on their assigned arm.

1. Compared to the control group, patients in the intervention arm will be more likely to have a screening test within 6 months (the percentage of patients who had either stool test or colonoscopy in each arm compared using a Fisher Exact test). We also used cumulative incidence function to compare time to screening completion.
2. Compared to the control group, patients in intervention arm will report higher SDM scores (compared mean scores using a two sample t-test).

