3. Compared to the control group, patients in the intervention arm will (3a) be more likely to have a clear preference for colon cancer screening (either colonoscopy or stool-based test) and (3b) have less decisional conflict (i.e. higher percentage of SURE top scores). We compared the percentage of patients with these outcomes between arms using Chi-square analyses.

In a pre-specified analysis, we explored the heterogeneity of treatment effects (HTE) to identify differential treatment effects among subgroups of patients stratified by sex as a biological

variable, age, race/ethnicity, education, overall health, prior screening history, COVID worry and interaction with decision coach. We used linear or logistic regression models to test the interaction between study arms and these factors. We highlighted the subgroups that presented differential effects regardless the significance of p values for the intervention and subgroup interaction. These results are exploratory in nature as the study was not powered for any of the subgroup analyses, and there was no attempt to control for potential biases.

CONSORT:

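### COVID-19 worry and coach contact arise after the intervention mailing yet serve as treatment-effect subgroups, and the SAP names neither anxiety nor cancer worry, which the protocol says the survey tracks

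*Protocol*

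**What the plan says.** **Subgroups.** The heterogeneity analysis in the SAP's Statistical methods lists, among other factors, "prior screening history, COVID worry and interaction with decision coach". Linear or logistic models test the interaction of each factor with study arm. Subgroups showing differential effects are highlighted whatever the interaction p value, and the results are labelled exploratory.

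**Covariates.** Under Outcomes the SAP writes: "Additional measures were collected to describe the sample and used as covariates including whether or not the patient had a CRC discussion". The same list includes "COVID-19 worry, decision worksheet use and decision coaching exposure". Only basic demographics are attributed to chart review.

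**Timing.** The SAP's Design section puts the survey "about 8 weeks after the intervention packet was mailed to their wave". The protocol's recruitment procedures for Aim 2 agree closely: "About 6-8 weeks after the mailing, the research coordinator will send a survey packet". Neither document describes a baseline survey of trial participants.

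**Anxiety and cancer worry.** The Aim 2 paragraph of the protocol's Research Design and Methods says: "We will invite patients to complete a survey to track SDM, decisional conflict, overall anxiety and cancer worry, preference for colonoscopy". The SAP's outcomes are screening uptake, the SDM Process Scale, SURE and screening preference, and its three hypotheses cover only these. Neither anxiety nor cancer worry is named anywhere in the SAP, and no reason is given.

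**The concern.** A treatment-effect subgroup should be defined by something that assignment cannot change. COVID-19 worry does not clearly meet that condition. The SAP's Background says that eliciting and addressing patients' concerns about testing may improve decisions, in a population that may hesitate to seek care during the pandemic. If the worksheet or the coach's call changes worry, high-worry intervention patients and high-worry controls are no longer comparable, and the difference between them mixes the treatment effect with a difference in who falls in the stratum. Coach contact is a plainer case, because it is delivered only to the intervention arm.

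The second part is a gap between the documents. The worksheet tells intervention patients of a wait of about 6 months for the first available colonoscopy, a possible delay of about 3 months after a positive stool test, and the option to wait a year. Whether this raises or lowers anxiety or cancer worry is a natural question, and the protocol planned to collect the constructs needed to answer it. The SAP gives them no analysis.

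**Working it through.** **1. When the two factors arise**

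| Factor | Apparent source | Time relative to assignment | Can assignment change it? |
|---|---|---|---|
| Sex, age, race/ethnicity | Chart review (basic demographics) | Fixed beforehand | No |
| COVID-19 worry | Survey (inferred) | About 8 weeks after the packet | Plausibly |
| Interaction with decision coach | Intervention delivery | After the packet | Yes; it is part of the intervention |

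The source of COVID-19 worry is an inference. The SAP lists it directly after the survey outcomes, assigns only demographics to chart review, and describes no earlier questionnaire.

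**2. The coach-contact interaction**

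Let A = 1 for intervention and C = 1 for coach contact. The interaction model contains A, C and A×C. If no control patient has coach contact, as the design implies, then C = 0 whenever A = 0. A×C then equals C for every patient. The two columns are identical and their coefficients cannot be separated. What remains is a comparison of coached with uncoached patients inside the intervention arm, and those groups were not randomized.

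**3. Which analyses are affected**

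Hypothesis 1 uses Fisher's exact test, hypothesis 2 a two-sample t-test and hypothesis 3 chi-square tests. None is adjusted, so the covariate list does not enter them. The exposure is the exploratory subgroup models and any adjusted model.

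**4. Reproducing the SAP's survey power**

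Inputs from Sample Size: 500 invited × 0.60 = 300 responses, 150 per arm at 1:1, and a difference of 0.32 SD. A two-sided 5% level is assumed, since the documents state none.

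- Standard error of a mean difference, in SD units: sqrt(1/150 + 1/150) = 0.1155.
- Power: Φ(0.32/0.1155 − 1.96) = Φ(0.81) = 79.1% (78.9% with the noncentral t), against 80% stated. The figure reproduces.

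**5. Precision for anxiety or worry in the same responders**

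- 95% confidence half-width: 1.96 × 0.1155 = 0.226, about 0.23 SD.
- Difference detectable with 80% power: (1.960 + 0.842) × 0.1155 = 0.32 SD.
- With the protocol's 450 responses (225 per arm): 2.802 × sqrt(2/225) = 2.802 × 0.0943 = 0.26 SD.

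A half-width of 0.23 SD does not by itself rule anything out. For example, excluding a rise of 0.5 SD needs an observed difference below 0.50 − 0.23 = 0.27 SD.

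**6. Whether the items were still planned when the survey went out**

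The last intervention wave was mailed on October 22, 2020. Eight weeks later is December 17, 2020. The protocol version is dated January 6, 2021 and still lists both constructs for the Aim 2 survey. This makes it less likely that they were an early idea already abandoned, but does not show that they were fielded.

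**The case against.** **The subgroup analysis is already hedged.** The SAP calls it exploratory, says it was not powered, and says no attempt was made to control for potential biases. That is a fair disclosure, and it limits the weight of the problem. It does not remove it: a reader of a highlighted subgroup will take it as effect modification, and the SAP highlights subgroups regardless of the p value. A general caution about bias does not tell that reader that two of the factors follow assignment.

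**No planned endpoint was lost.** The protocol's Aim 2 hypotheses are that intervention patients "report higher shared decision making; (b) have stronger intention to follow through with colon cancer screening", and have less decisional conflict. Anxiety and cancer worry carry no Aim 2 hypothesis; in the Specific Aims they stand under Aim 1. This stands. The gap concerns a survey measure without an analysis.

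**The items may have been collected or compared.** The SAP's list of additional measures is not worded as exhaustive, and its balance comparison of sample characteristics might show COVID-19 worry by arm. Both are possible. A balance table would present worry as a characteristic rather than a result, and would still not name anxiety or cancer worry.

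**Two stronger readings are not supported.** A reader might infer that the protocol names psychological harm from the intervention as a risk and then fails to assess it. The sentence on this reads: "To address issues of psychological discomfort, research assistants will inform patients that they may refuse to answer any question". Its remedy concerns survey questions, and Data and Safety Monitoring likewise refers to being upset by a survey question. Nothing there identifies distress from the worksheet or coaching. A reader might also infer that the trial can report only benefit or no difference. It can do otherwise: uptake, SDM scores, clear preference or SURE top scores could each come out lower in the intervention arm.

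**Additions now would be post hoc.** The SAP is dated August 25, 2021, is written in the past tense, and follows the mailings. This stands and should be stated in the report.

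**Conclusion.** The point holds for two limited matters. First, COVID-19 worry and coach contact are post-randomization factors used as treatment-effect subgroups and listed as covariates. Results within those strata can be biased, and the coach-contact interaction cannot be estimated if no control patient had coach contact. The direction and size of any bias from COVID-19 worry cannot be derived from the documents. The tests of hypotheses 1 to 3 are unaffected.

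Second, overall anxiety and cancer worry are planned for the Aim 2 survey but absent from the SAP, so as written no between-arm conclusion on them will be drawn. If fielded and scored as continuous measures, they could be compared with a half-width of about 0.23 SD.

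The conclusion assumes that COVID-19 worry came from the post-mailing survey, that 150 patients per arm responded, and a two-sided 5% level. It is worth correcting because the change is cheap, not because the main results are in doubt.

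**What to change.** 1. Remove COVID-19 worry and interaction with the decision coach from the treatment-effect subgroups and from any adjusted model. Alternatively, keep them under a separate label as post-randomization associations that are not evidence of effect modification. If COVID-19 worry was in fact measured before the mailing, state when and how; its objection then falls away.
2. Report COVID-19 worry by assigned arm with a mean or risk difference and 95% confidence interval, labelled descriptive and post hoc and kept outside the hypothesis tests.
3. State whether overall anxiety and cancer worry were fielded in the Aim 2 survey. If so, report them in the same way. If not, say so and draw no conclusion on anxiety or worry.

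**Cost.** One or two exploratory subgroups are lost, up to three descriptive comparisons are added, and those comparisons are post hoc. If the items were fielded, no new data are needed; if they were not, the change for those two measures is a sentence of disclosure.

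### Aim 3 compares wait times but defines a wait only for patients who had a colonoscopy, with no start date and no rule for patients without one at 12 months or screened another way

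*Protocol*

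**What the plan says.** The Protocol's Specific Aims set Aim 3 as: "Follow all patients on the waitlist and examine wait times and completed colonoscopies to determine whether these differ by patient characteristics". The comparison is by gender, age, race and ethnicity and is to be adjusted for cancer risk. There are therefore two outcomes, wait and completion, each to be compared by the same characteristics.

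Under Research Design and Methods, the Aim 3 paragraph says "we will follow all MGH patients who had their screening or surveillance colonoscopy delayed for 12 months" and that staff "will document receipt of colonoscopy or other colon cancer screening test". It then gives the only rule for the wait: "if they got a colonoscopy, will calculate the wait time for colonoscopy for all of the patients on the waitlist". The variables listed are: "We will track demographic information, age, gender, race and ethnicity, primary language, zip code". On cohort size: "We estimate that there are about 5,000 patients who have had their colonoscopy delayed".

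The Protocol names no model, summary statistic, start date or censoring rule for Aim 3. The SAP does not fill the gap. Its title limits it to the randomized trial, and the cumulative incidence function it mentions is for time to screening between the trial arms.

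**The concern.** The rule makes the wait conditional on having had a colonoscopy. A patient still without one at 12 months has waited at least 12 months, but under this rule that patient has no value. If the comparison is run on the available values, each group is represented only by those who got through within the window, and the group with poorer access loses more of its long waits. Differences between groups then shrink.

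Non-completion is unlikely to be rare. The Protocol's background section expects volume to recover to about 66% of its former level within 2-3 months and not to return fully within the next year. It also cites a poll in which most patients said they were unlikely to visit a hospital. The trial's worksheet gives about 6 months as the wait for a first available colonoscopy and lists a one-year delay as an option.

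The start of the clock also matters. The master waitlist combines postponed procedures, unprocessed referrals and patients who should have been contacted but were not. These routes have no common natural start date.

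At stake is the reading of a stated aim. A report of similar waits by race or ethnicity could be an artefact of the definition, and the Protocol says the findings will bear directly on managing the backlog.

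**Working it through.** The Protocol gives no power, expected wait or expected difference for Aim 3, so there is no planned figure to reproduce. The check asks how far a completers-only wait can depart from a wait that uses everyone.

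**Inputs.** The 12-month window is from the Protocol. Constant hazards and all completion rates and medians below are assumptions. The 6-month median in the second set is chosen to match the wait quoted in the Aim 2 description.

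**Formulas.** With completion c at 12 months and hazard λ per month:

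- λ = −ln(1 − c)/12
- completer-only mean = 1/λ − 12(1 − c)/c
- restricted mean wait to 12 months, all patients = c/λ

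**Main illustration, 70% against 40% completion.**

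- c = 0.70: λ = 1.204/12 = 0.1003. Completer mean = 9.97 − 5.14 = 4.82. Restricted mean = 0.70/0.1003 = 6.98.
- c = 0.40: λ = 0.5108/12 = 0.0426. Completer mean = 23.49 − 18.00 = 5.49. Restricted mean = 0.40/0.0426 = 9.40 (unrounded λ).

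The gap is 9.40 − 6.98 = 2.42 months using everyone and 5.49 − 4.82 = 0.67 month using completers. The completers-only comparison shows 0.67/2.42, or about 28%, of the gap visible within the window.

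**Range over other assumed medians**, against a reference group with median 6 months (completion 75.0%, completer mean 4.66, restricted mean 6.49):

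| True median (months) | Completion at 12 months | Completer mean | Gap in completer mean | Restricted mean | Gap in restricted mean |
|---|---|---|---|---|---|
| 8 | 64.6% | 4.98 | 0.32 | 7.46 | 0.97 |
| 12 | 50.0% | 5.31 | 0.65 | 8.66 | 2.17 |
| 18 | 37.0% | 5.54 | 0.88 | 9.61 | 3.12 |
| 24 | 29.3% | 5.65 | 0.99 | 10.14 | 3.65 |

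**Groups that differ only in the share who ever return** (100%, 80%, 60%; median 6 months among returners). The completer median is 4.07 months in all three, so the wait comparison shows nothing. Completion is 75%, 60% and 45%, and the overall median waits are 6.0, 8.5 and 15.5 months.

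In every one of these scenarios the completion outcome does show the difference. The loss is confined to the wait-time result.

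**The case against.** The strongest reply is that Aim 3 names completion in the whole followed cohort as an outcome, compared by the same characteristics. A reader might infer that the disparity comparison as a whole conditions on completion and hides the patients still waiting. The documents do not support that: non-completers are counted in the completion half, where 70% against 40% would be plain.

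A reader might also infer that the plan says to drop non-completers. It does not. The sentence that begins with the condition ends by referring to everyone on the waitlist, and all are followed for 12 months, so a censored analysis is compatible with the text. Completers-only is the natural reading of the condition but is not a stated method. What stands is that the sentence conflicts with itself and no rule resolves it.

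Other stronger readings also fail:

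- **A much larger loss.** Under the main illustration the true medians are 6.9 and 16.3 months, and setting that 9.4-month gap against 0.7 would look dramatic. It compares medians with means, and 16.3 months lies beyond follow-up, so censoring at 12 months could not recover it.
- **Reversal.** This can happen. If all of one group return (median 6 months) but only half of the other do (median 5 among returners), completer means are 4.66 and 4.41 while completion is 75% and 41%. That is a constructed case, and nothing in the documents points to it.
- **No cancer-risk variable.** The tracked list is introduced as demographic information, not as a full covariate list. First screening or recommended follow-up interval is already used for eligibility in Table 1. The covariate is unnamed, not absent.

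It is also fair that the wait among those who had a colonoscopy is a legitimate descriptive figure when shown with completion, and that some non-completers will have chosen to delay or to use another test. That supports stating how each is handled; it does not make a completers-only comparison a measure of access.

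**Conclusion.** The point holds as a gap in the definition and analysis of one Aim 3 outcome. The wait is defined only for patients who had a colonoscopy. No start date is given, and there is no rule for patients without one at 12 months or screened by another test. If the comparison is run on completers, it would understate differences between groups: in the main illustration 0.7 month is shown against 2.4 months when everyone is used. Across the assumed medians of 8 to 24 months against 6, the completer-mean gap is 0.3 to 1.0 month where the restricted-mean gap is 1.0 to 3.7.

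These sizes rest on constant hazards and assumed completion rates. The shrinkage appeared in every scenario with differing rates, but its amount in this cohort cannot be known from the documents. Reporting completion separately limits the damage without correcting the wait-time result. Aim 3 is descriptive chart review, so the change is advisable and not critical.

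**What to change.** State the Aim 3 analysis in the Protocol or in a short supplement to the SAP:

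- Include all waitlist patients (about 5,000) and analyse time to colonoscopy, censored at 12 months.
- Define one start date that applies to all three routes onto the list, for example the date of list entry.
- Present cumulative incidence curves by patient characteristic and fit a Cox or cause-specific model. A restricted mean wait to 12 months gives a summary in months that stays within follow-up.
- State how other screening tests are handled. Treating them as a competing event is one option, but a positive stool test can lead to a colonoscopy, so the plan should say whether follow-up for colonoscopy continues after such a test.
- Name first screening or recommended follow-up interval, already used for eligibility, as the cancer-risk covariate.
- Report the result beside the completion comparison. Any wait among completers should be labelled as descriptive.

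The cost is a paragraph of wording and a little more analysis. The dates of other tests may also be needed from the same chart review. No patients or procedures are added.
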